8.4 Procedure at disease progression

Progression events should be imaging defined in all tumour types according to RECIST criteria. In addition, for prostate cancer patients progression by bone scan and PSA progression will be considered. On the rare occasions that progression cannot be measured by scan or biochemical failure (prostate only), clinical evidence of widespread progression will count as a PFS event.

Participants should be treated according to local clinical judgement at disease progression. Following progression, participants will continue to be followed-up for FFWM and overall survival. Imaging and visits following progression can be according to local practice and do not need to follow the protocol specified visit time points, however information regarding FFWM and survival status should be entered onto the eCRFs.

The FFWM endpoint is defined as radiological evidence that the patient has 4 or more metastatic sites and/or the site(s) of disease progression are not suitable for radical salvage therapy (e.g. surgery, RFA or SBRT).

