11.1.2 Sample size

This phase II screening study has been designed with a primary endpoint of PFS, and relaxed one-sided $\alpha=0.20$ and $\beta=0.20$ (13). The control arm PFS is estimated based on the expected contribution of each primary tumour site to the overall final sample size. Based on observed recruitment in the first year this is estimated at 75% prostate, 14% breast and 11% lung. Assuming a median PFS of 5 months for NSCLC, 12 months for breast and 18 months for prostate patients (14-22), it is estimated that the median PFS in the control group after randomisation will be 16 months. The phase II SABR-COMET trial targets a hazard ratio (HR) for OS of 0.6 (23). For CORE, a more conservative effect size has been chosen reflecting clinical opinion of what would constitute a PFS signal worthy of a phase III OS trial. In order to detect a HR of 0.75 for improvement of PFS i.e. extending the median cohort PFS by 4 months in the experimental arm with 80% power, a total of 230 patients are required (138 events). Assuming a 5% rate of patients lost to follow up at the point of data analysis, a total of 242 patients will be required (121 per treatment group). Dependent on observed rates of accrual this total may increase to a maximum of 270 to allow for each cohort to achieve a minimum of 50 patients. The sample size calculations, made using the *artsurv* command in Stata version 13, assume 50% recruited in both years 1 and 2 and 12 months of additional follow up.

The decision rule to proceed to phase III will be based on a 3 outcome design. An overall result significant at the 10% level would support continuation to phase III; significance between 10% and 20% would require supportive evidence from secondary endpoints with a particular emphasis on local tumour control and FFWMD. If the significance is >20% then the study will not progress to phase III unless there is clear

heterogeneity of outcomes between the 3 tumour subgroups supporting a signal in selected tumour sites in which case consideration would be given to progressing to an extended phase 2 evaluation for that tumour site alone.

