11.2.2 Secondary endpoints

Recruitment rate is defined as the proportion of patients recruited to the trial. The denominator is the total number of patients required (i.e. 206 patients).

SBRT delivery is based on the proportion of patients allocated SBRT who received SBRT in the absence of new developing widespread disease and within the dosimetric constraints outlined in the SBRT protocol. The denominator is the number of patients allocated SBRT.

Overall survival is defined as time from randomisation until the time of death from any cause

Local lesion control is defined as time from randomisation until radiological evidence of progression at the treated site.

Clinician reported acute and late radiation related toxicity will be graded using NCI CTCAE v4.0/RTOG systems. Acute events are defined as those occurring up to 3 months follow up; late events are reported from 6 months post randomisation.

Patient reported quality of life will be measured using the EORTC QLQ C30 and EQ5D.

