11.2.4 Statistical analysis plan

Analyses will be according to the intention-to-treat method. Time to event endpoints will be presented using Kaplan Meier methods with treatment effects presented as relative and absolute estimates. Hazard ratios will be derived from Cox proportional hazards models stratified by disease site. The time point of interest is 1 year from randomisation. The log rank test will be used to compare treatment groups stratified by disease site. For PFS, patients who are event free at time of analysis will be censored using the date of last disease assessment (imaging for breast, NSCLC and PSA assessment for prostate). An appropriate alternative method will be used if there is evidence of non-proportional hazards.

Acute and late toxicity will be summarised as frequencies and percentage at each time point. Non-haematological grade 2 or greater (G2+) toxicities related to SBRT treatment are of primary interest. The proportion experiencing G2+ will be presented by treatment group and comparisons made between treatments using Fishers exact tests, separate comparisons will be made of acute and late toxicity.

Quality of life data will be analysed using standard algorithms to derive scores and handle missing data according to the EORTC scoring manual. Descriptive statistics (median, IQR, range) will be presented by treatment group at each time-point. Statistical comparisons will be made at 12 and 18 months. Analyses to account for the longitudinal nature of the data may also be used.

A planned exploratory analysis will be performed to investigate the treatment effect in each primary site subgroup. This will be summarised with a hazard ratio and compared in each subgroup to look for consistency of effect (accepting that there will be little power for a formal test of heterogeneity). There will be very limited power and much uncertainty about these estimates, and therefore they will be interpreted with caution.

Further details of analysis methods will be specified in a Statistical Analysis Plan in accordance with ICR-CTSU Standard Operating Procedures.

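### Local lesion control runs on past a progression elsewhere, but after first progression the protocol secures neither imaging nor recording of the treated lesions, so local failure may be somewhat understated

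*Protocol*

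**What the plan says.** Section 11.2.2 gives the endpoint a start and an event: "Local lesion control is defined as time from randomisation until radiological evidence of progression at the treated site". It names no end at progression elsewhere.

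Section 8.4 sets what happens after progression at any site. On the schedule: "Imaging and visits following progression can be according to local practice and do not need to follow the protocol specified visit time points". On purpose: "Following progression, participants will continue to be followed-up for FFWM and overall survival". On data: "information regarding FFWM and survival status should be entered onto the eCRFs". Local control appears in none of the three. Sections 8.4 and 11.2.1 also allow PSA progression to be considered for prostate patients.

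Section 11.2.4 covers the analysis: "Time to event endpoints will be presented using Kaplan Meier methods", with 1 year from randomisation as the time point of interest. Its only censoring rule is for another endpoint: "For PFS, patients who are event free at time of analysis will be censored using the date of last disease assessment". For prostate patients that assessment is the PSA test. Further methods are left to a SAP, which is not at hand.

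Section 11.1.2 uses the endpoint. When PFS significance lies between 10% and 20%, moving to phase III needs "supportive evidence from secondary endpoints with a particular emphasis on local tumour control and FFWMD".

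**The concern.** Section 8.4 lists the endpoints that continue after progression and omits one whose definition also continues. A treated lesion that fails after a new lesion appears elsewhere need not be scanned on schedule, and its status is not among the items requested.

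The gap is widest in prostate patients, who are 75% of the expected sample. A PSA progression says nothing about the treated lesion, yet it can release the patient from scheduled imaging. Routine prostate scans fall only at 6, 12 and 24 months (8.3.4), so a PSA progression before month 12 can remove the scheduled scan at the 1-year time point.

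The error runs one way. Missed failures make SBRT look better on an endpoint that supports the phase III decision in the intermediate zone. A SAP can choose a censoring date, but it cannot recover lesion status that was never requested.

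**Working it through.** **The plan's own figure.** The protocol gives no figure for local control or for this bias. Its PFS design does reproduce, so its PFS assumptions can be used here. Schoenfeld events = 4(z₀.₈₀ + z₀.₈₀)² / (ln 0.75)² = 4(1.683)² / 0.0828 = 137, against 138 stated.

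**Inputs from the protocol**
- Site mix 75% prostate, 14% breast, 11% NSCLC; control medians 18, 12 and 5 months; HR 0.75 (11.1.2).
- Local control at 6 years of 87% (breast) and 65% (non-breast) in a cited SBRT series (1.2).
- Time point of 1 year (11.2.4).

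**Assumptions not in the protocol**
- Exponential times and a constant local-failure hazard.
- Worst case: patients stay at risk after progression and no later local failure is recorded.

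**Step 1: hazards per month.** Progression in the SBRT arm is k = ln 2 × 0.75 / median: 0.0289 (prostate), 0.0433 (breast), 0.1040 (NSCLC). Local failure is λ = −ln(6-year local control)/72: 0.00193 (87%) and 0.00598 (65%).

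**Step 2: time before first progression.** By time T each site contributes (1 − e^(−kT))/k.
- 12 months: 0.75×10.14 + 0.14×9.36 + 0.11×6.86 = 9.67 of 12 months, so 19% is without secured ascertainment.
- 24 months: 0.75×17.31 + 0.14×14.92 + 0.11×8.82 = 16.04 of 24 months, so 33%.

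**Step 3: understatement of local failure.** True failure by T is 1 − e^(−λT). Recorded failure is computed in two ways:
- (a) Local failure is added to the full PFS hazard: Σ w·λ/(k+λ)·(1 − e^(−(k+λ)T)).
- (b) Local failure is already inside the PFS hazard, since PFS counts progression at any site: Σ w·λ·(1 − e^(−kT))/k.

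| 6-year local control | T (months) | True | Recorded (a) | Relative (a) | Recorded (b) | Relative (b) |
|---|---|---|---|---|---|---|
| 87% | 12 | 2.29% | 1.85% | 19% | 1.87% | 18% |
| 65% | 12 | 6.93% | 5.60% | 19% | 5.79% | 16% |
| 87% | 24 | 4.54% | 3.04% | 33% | 3.10% | 32% |
| 65% | 24 | 13.38% | 9.03% | 32% | 9.60% | 28% |

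At 12 months the absolute gap runs from 2.29 − 1.87 = 0.4 to 6.93 − 5.60 = 1.3 percentage points.

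**Step 4: sensitivity**
- Local failure of 15% per year (an assumption above the section 1.2 rates), version (b): 13% at 12 months and 22% at 24 months.
- One SBRT-arm median of 20 months (16 + 4) or 21.3 months (16/0.75) in place of the site mix, version (b), section 1.2 rates: 14% to 17% at 12 months and 26% to 31% at 24 months.
- Half of the later failures recorded: every relative figure halves, so at most about 10% at 12 months.
- NSCLC alone (SBRT-arm median 5/0.75 = 6.7 months), version (b): about 41% to 42% at 12 months, in 11% of patients.

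**Step 5: with censoring.** Censoring at the last scheduled lesion assessment or at progression elsewhere, with the two processes independent, gave 10.1% in simulation against a true 10.0% at 12 months.

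**The case against.** A reader might infer that patients go on accruing locally controlled time until last survival contact, and that local failure is therefore understated by about a third. The protocol supports neither statement. Section 11.2.2 states an origin and an event but no censoring rule, and section 11.2.4 defers detail to a SAP that may well censor at the last lesion scan. About a third appears only near 24 months, with patients kept at risk and no later failure recorded. The plan's stated time point is 1 year. About a third is also close to the share of SBRT-arm patients expected to have progressed or died by 12 months (35% on the site mix), but that share is not the bias.

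Zero recording is also too harsh. Imaging continues under local practice. Judging widespread disease needs radiological evidence and will often show the treated lesion. Repeat SBRT requires control of the sites already treated (9.1.6), though only for patients offered it. The eCRF is not shown and can be changed without a protocol amendment (14.3), so it may already hold lesion status. Finally, local control is a descriptive rate in the SBRT arm, and section 11.1.2 sets no numerical threshold for it, so nothing shows that about one percentage point would change the decision.

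These points settle the size: the figures above are upper bounds under their assumptions. They do not close the gap in section 8.4. Censoring at the last lesion scan works only if local failure is independent of progression elsewhere, which the protocol does not establish.

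**Conclusion.** The point holds as a gap in data collection. The endpoint continues past progression elsewhere, while the scheduled imaging and the requested data do not cover it. Local failure may be understated, in the direction that favours SBRT.

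The size is modest at the time point that matters. The worst case is about a fifth in relative terms at 1 year (13% to 19%, depending on how local failure is separated from PFS and on the local failure rate assumed). With the section 1.2 rates that is roughly 0.4 to 1.3 percentage points. At 2 years the worst case is about 22% to 33%. These figures rest on the plan's PFS assumptions, constant hazards, patients kept at risk and no later failure recorded. Deaths within PFS are not separated out, and doing so would lower them. If local failure is more likely after progression elsewhere, some understatement would remain even with censoring, by an amount the protocol cannot give.

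This is a cheap improvement to a supportive endpoint and does not touch the primary analysis.

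**What to change.** - **Section 8.4:** add the status of each treated lesion (controlled or progressed, with scan date) to the data entered after progression. Take it from scans already done under local practice, with no extra imaging.
- **Section 11.2.4:** extend the last-assessment censoring rule to local lesion control, using the date of the last scan that imaged the treated lesion. The PFS rule cannot simply be copied, because its prostate date is a PSA test, which does not show the lesion.

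How death is handled can be left to the SAP.

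The cost is one more eCRF item and one sentence in each section. The reported local control rate may become slightly less favourable. Some informative censoring will remain, because scans under local practice will not be evenly timed; the new item reduces it but does not remove it.

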11.2.3 Exploratory endpoint

Freedom from widespread metastatic disease (FFWMD) will be measured from the time of randomisation until radiological evidence of disease progression, which is not suitable for radical salvage therapy (e.g. surgery, RFA or SBRT). Widespread metastatic disease is defined as greater than or equal to 4 metastatic sites, regional or distant, or a combination thereof. This will reflect the trial entry criteria, i.e. eligible patients must have ≤ 3 sites of metastatic disease relapse, all technically suitable for salvage therapy.

11.2.4 Statistical analysis plan

Analyses will be according to the intention-to-treat method. Time to event endpoints will be presented using Kaplan Meier methods with treatment effects presented as relative and absolute estimates. Hazard ratios will be derived from Cox proportional hazards models stratified by disease site. The time point of interest is 1 year from randomisation. The log rank test will be used to compare treatment groups stratified by disease site. For PFS, patients who are event free at time of analysis will be censored using the date of last disease assessment (imaging for breast, NSCLC and PSA assessment for prostate). An appropriate alternative method will be used if there is evidence of non-proportional hazards.

Acute and late toxicity will be summarised as frequencies and percentage at each time point. Non-haematological grade 2 or greater (G2+) toxicities related to SBRT treatment are of primary interest. The proportion experiencing G2+ will be presented by treatment group and comparisons made between treatments using Fishers exact tests, separate comparisons will be made of acute and late toxicity.

Quality of life data will be analysed using standard algorithms to derive scores and handle missing data according to the EORTC scoring manual. Descriptive statistics (median, IQR, range) will be presented by treatment group at each time-point. Statistical comparisons will be made at 12 and 18 months. Analyses to account for the longitudinal nature of the data may also be used.

A planned exploratory analysis will be performed to investigate the treatment effect in each primary site subgroup. This will be summarised with a hazard ratio and compared in each subgroup to look for consistency of effect (accepting that there will be little power for a formal test of heterogeneity). There will be very limited power and much uncertainty about these estimates, and therefore they will be interpreted with caution.

Further details of analysis methods will be specified in a Statistical Analysis Plan in accordance with ICR-CTSU Standard Operating Procedures.

11.2.5 Interim analyses and stopping rules

With the early assessment of feasibility there will be opportunities to stop the trial early should accumulating data justify this based on recruitment, treatment deliverability or toxicity.

Feasibility of recruitment: The IDMC and TSC will monitor recruitment rates and may recommend on trial closure if these are significantly less than expected and continuation of the trial is felt futile. Recruitment feasibility will be assessed by the number of open centres, patient acceptance rates and the number of patients randomised. For example, target recruitment is 20% year 1, 30% year 2 and 50% year 3, if actual recruitment is not at least half of what is targeted (i.e. at least 10% in year 1) then consideration would be given for closing the study due to it not being feasible to complete within a timely manner. If the acceptance rate amongst eligible patients falls below 50% this will trigger review of the recruitment process at sites by the Trial Management Group; if acceptance rates fall below 33% this will trigger referral to the TSC.

Deliverability of SBRT: At least 85% of patients randomised to SBRT + SOC are anticipated to receive their allocated SBRT treatment in the absence of new developing widespread disease and within the dosimetric constraints outlined in the SBRT protocol.

Safety: The IDMC will monitor safety with a formal review after 10, 34 and 51 patients have been treated with SBRT and followed up for 6 months. Consideration would be given to stopping the trial if the late grade 4/5 toxicity rate exceeds 5% in the experimental arm.

There are no early stopping rules for efficacy planned during the phase II component of this trial.

12 TRIAL MANAGEMENT

12.1.1 Trial Management Group (TMG)

A Trial Management Group (TMG) will be set up and will include the Chief Investigator, ICR-CTSU Scientific Lead, Co-investigators and identified collaborators, the Trial Statistician and Trial Manager. Principal Investigators and key study personnel will be invited to join the TMG as appropriate to ensure representation from a range of sites and professional groups. Where possible, membership will include a lay/consumer representative. The TMG will meet at regular intervals, and at least annually. Notwithstanding the legal obligations of the Sponsor and Chief Investigator, the TMG have operational responsibility for the conduct of the trial. The Committee's terms of reference, roles and responsibilities will be defined in a charter issued by ICR-CTSU.

12.1.2 Trial Steering Committee (TSC)

A Trial Steering Committee (TSC) will be set up and will comprise an independent Chairman and at least 2 further independent members with clinical or statistical expertise (at least 1 member must be a statistician). The TSC will meet at regular intervals, and at least annually. The TSC will provide expert independent oversight of the trial on behalf of the Sponsor and funder. The Committee's terms of reference, roles and responsibilities will be defined in charter issued by ICR-CTSU.

12.1.3 Independent Data Monitoring Committee (IDMC)

An Independent Data Monitoring Committee (IDMC) will be set up to monitor the progress of the trial and will comprise a Chairman and at least 2 further members with clinical or statistical expertise (at least 1 member must be a statistician). Membership of the IDMC will be proposed by the TMG and approved by the TSC.

The IDMC will meet in confidence at regular intervals, and at least annually. In addition, the IDMC will monitor safety with a formal review after 10, 34 and 51 patients have been treated with SBRT and followed up for 6 months (see section 12.5). A summary of findings and any recommendations will be produced following each meeting. This summary will be submitted to the TMG and TSC, and if required, the main REC and the MHRA.

The IDMC will reserve the right to release any data on outcomes or side-effects through the TSC to the TMG (and if appropriate to participants) if it determines at any stage that the combined evidence from this and other studies justifies it.

The Committee's terms of reference, roles and responsibilities will be defined in a charter issued by ICR-CTSU.

13 RESEARCH GOVERNANCE

13.1 Sponsor responsibilities

The Sponsor of this clinical trial is the Royal Marsden NHS Foundation Trust

A coordinating group in each participating (non-UK) country will be delegated responsibility for trial initiation and conduct in that country on behalf of the Sponsor, as defined in an agreement between the Sponsor and the coordinating group.

13.2 Participating site responsibilities

Responsibilities delegated to participating sites are defined in an agreement between the Sponsor and the individual site.

Responsibilities of participating sites are defined in an agreement between the individual participating site and the Sponsor (UK) or the coordinating group delegated that responsibility by the Sponsor (non-UK).

14 TRIAL ADMINISTRATION & LOGISTICS

14.1 Site activation

Before activating the trial, participating sites are required to sign an agreement accepting responsibility for all trial activity which takes place within their site.

Sites may commence recruitment once the site agreement has been signed by all required signatories, the required trial documentation is in place (as specified by ICR-CTSU) and a site initiation (visit or teleconference) has taken place. Site initiation visits will be conducted at sites where the Principal Investigator has requested one or where ICR-CTSU deems it is appropriate.

14.2 Investigator training

Each centre will complete the comprehensive pre-trial section of the quality assurance programme prior to commencing recruitment as detailed in the Radiotherapy Planning and Delivery Guidelines. The radiotherapy QA programme will continue throughout the trial, with investigator training as required.

14.3 Data acquisition

Electronic (e) Case Report Forms (CRF) will be used for the collection of trial data. Data from all collaborating groups will be held centrally by the ICR-CTSU.

CORE trial data should be reported to the ICR-CTSU in a timely manner. ICR-CTSU will provide guidance to sites to aid the completion of the eCRFs. The Trial Management Group reserves the right to amend or add to the eCRF template as appropriate. Such changes do not constitute a protocol amendment, and revised or additional forms should be used by sites in accordance with the guidelines provided by ICR-CTSU.

